
based on the observed proportion of patients with ppPASI50 at week 16 for BI 655130 and placebo will be assessed descriptively, for the Full Analysis Set (FAS), and 95% Wilson confidence intervals (CIs) will also be provided. The FAS comprises all participants who were randomised, received at least one dose during the trial, and had a baseline measurement for the primary endpoint. The influence of the stratification variable on the primary endpoint will be characterized in exploratory analyses.
 
Safety data will be presented using descriptive methods.
			

FLOW CHART

Trial Periods	Screening ¹	Randomised Treatment Period										Post treatment follow-up	
		2 ²	3	4	5	6	7	8	9	10	11 PE ³	12	13 EOT ⁴
Visit	1												
Week	-4 to -1				2	4	6	8	10	12	16	24	32
Day	-28 to -7	1	4±2	8±3	15±3	29±3	43±3	57±3	71±3	85±3	113±3	169±7	225±7
Informed Consent	X												
Inclusion/exclusion criteria	X	X											
Demographics, Medical History	X												
Physical Examination	X ^{12,C}	X ^T	X ^T	X ^T	X ^T	X ^T	X ^T	X ^T	X ^T	X ^T	X ^C	X ^T	X ^{12,C}
Vital Signs	X	X	X	X	X	X	X	X	X	X	X	X	X
Pregnancy testing ⁵	X ^s	X ^{u,(s)}				X ^{u,(s)}		X ^{u,(s)}		X ^{u,(s)}	X ^{u,(s)}	X ^{u,(s)}	X ^{u,(s)}
Safety Laboratory tests	X	X	X	X	X	X	X	X	X	X	X	X	X

Proprietary confidential information © 2018 Boehringer Ingelheim International GmbH or one or more of its affiliated companies

Trial Periods	Screen- ing ¹	Randomised Treatment Period										Post treatment follow-up		
		1	2 ²	3	4	5	6	7	8	9	10	11 PE ³	12	13 EOT ⁴
Week	-4 to -1					2	4	6	8	10	12	16	24	32
Day	-28 to-7	1	4±2	8±3	15±3	29±3	43±3	57±3	71±3	85±3	113±3	169± 7	225±7	
Assign/Administer study drug		X					X		X		X			

Palmoplantar Pustular Psoriasis Area and Severity Index (ppPASI)	X	X	X	X	X	X	X	X	X	X	X	X	X	X
PPP Physician Global Assessment (pppPGA)	X	X	X	X	X	X	X	X	X	X	X	X	X	X

12-lead ECG	X	X				X		X		X	X	X	X	X
Local Tolerability		X				X		X		X				
Adverse events	X	X	X	X	X	X	X	X	X	X	X	X	X	X
Concomitant Therapy	X	X	X	X	X	X	X	X	X	X	X	X	X	X
Completion of participation ⁴														X

Footnotes:

¹ The time window for Visit 1 may be extended at the discretion of the Local Clinical Monitor (CML) in conjunction with the TCM (Trial Clinical Monitor) on a case by case basis.

² Day of Randomisation / Day of first administration of randomised medication.

³ PE – Primary Endpoint Visit.

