3.2 DISCUSSION OF TRIAL DESIGN, INCLUDING THE CHOICE OF CONTROL GROUP(S)

This phase IIa trial is the first study with BI 655130 to be conducted in PPP patients. Current safety data about BI 655130 were obtained from a previous first-in-man single dose phase I trial 1368.1 and the multiple raising dose trial 1368.2 both carried out in healthy volunteers. BI 655130 was safe and well tolerated in all dose groups tested in 1368.1 and in all dose group tested so far in 1368.2 (10 mg/kg multiple dosing and 20 mg/kg single dose. 20 mg/kg multiple dose group has been approved and is currently ongoing.

Non-clinical safety data are limited as BI 655130 could not be directly tested in preclinical toxicity studies (a surrogate antibody specific to mouse was used instead). The main objective of this phase IIa trial is to investigate proof of concept (safety and efficacy) and tolerability of BI 655130 in patients with PPP. Pharmacokinetics and pharmacogenomics will also be evaluated.

Both patients who have a pure palmoplantar pustulosis (PPP) presentation and those patients with a mixed pustulosis and psoriasis presentation on less than 10% of the BSA will be included in this study.

A placebo control group is necessary and is included in this trial because there are currently no clinical trial data available in the published literature that describes a placebo response on the primary efficacy endpoint in the population of patients with palmoplantar pustulosis.

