5.3.2 Vital Signs

Vital signs evaluations will be performed at visits as shown in the Flow Chart. This includes measuring temperature, pulse rate, systolic/diastolic blood pressure and respiratory rate. Respiratory rate, pulse rate, and blood pressure will be measured after patients have been sitting comfortably for at least five minutes. All recordings should be made using the same type of blood pressure recording instrument on the same arm if possible.

Measurement of vital signs should precede blood sampling to avoid the impact of blood sampling on the vital measurements. At visits with study drug administration vital signs will be assessed pre-dose, at 5 minutes and approximately 120 minutes after study drug administration.

Patients should be closely monitored for signs and symptoms of hypersensitivity reactions for approximately 2 hours after the study drug administration. Hypersensitivity reactions should be treated according to medical standards. Pre-medications for further injections might be considered and will be agreed on between investigator and BI clinical monitor.

Anaphylaxis is a serious allergic reaction that is rapid in onset and may cause death [R11-4890]. To be able to prospectively define and assess any potential cases of anaphylaxis, the clinical criteria for diagnosis of anaphylaxis defined in [Section 10.1](#) are to be considered.

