5.3.5.2 Local tolerability

Local tolerability will be assessed by the investigator according to ‘swelling’, ‘induration’, ‘heat’, ‘redness’, ‘pain’, or other findings’ at the times indicated in the Flow Chart.

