6.0 INVESTIGATIONAL PLAN

6.1 VISIT SCHEDULE

All patients are to adhere to the visit schedule as specified in the [Flow Chart](#). Investigators are to encourage adherence by the patient to protocol specific activities. Each visit date (with its window) is to be counted from Day 1. The acceptable time windows for follow-up visits and end of trial examination are given in the Flow Chart. All deviations from the planned visit schedule will be documented. If any visit has to be rescheduled, subsequent visits should follow the original visit date schedule. Additional visits for the purpose of re-testing of laboratory parameters or AE monitoring may be included as deemed necessary by the investigator.

If a patient misses an appointment, it will be rescheduled if possible. The relevance of measurements outside the permitted time windows will be assessed no later than at the last Blinded Report Planning Meeting.

Study measurements and assessments are scheduled to occur 'before' trial medication administration at dosing visits and are to be performed and completed prior to the trial drug administration. For planned individual plasma concentration sampling times refer to the Flow Chart. At non-dosing visits sampling should be done after other study procedures have concluded. Sampling times will be recorded and used for determination of pharmacokinetic parameters.

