6.2 DETAILS OF TRIAL PROCEDURES AT SELECTED VISITS

Study procedures to be performed at each visit are listed in the Flow Chart and respective protocol sections. Additional details on procedures at selected visits are provided below.

Measurement of vital signs should precede blood sampling and be assessed pre-dose at all dosing visits.

The following sequence of procedures at each visit (where applicable) is recommended:

2. AE/local tolerability and concomitant therapy collection
3. Physical examinations
4. pppPGA, ppPASI

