6.2.2 Treatment period(s)

When eligibility of the patient to participate in the trial is confirmed, randomisation via IRT will be performed at Visit 2. The treatment period is from Visit 2 to Visit 10, followed by the primary endpoint visit at week 16 (Visit 11). Procedures described in the Flow Chart for each visit should be performed.

At visits during the treatment period, venepuncture (i.e. safety laboratories, should be the last procedures performed prior to study drug administration. Only after all blood specimens are collected, will each eligible patient receive a dose of the assigned trial medication. Trial medication will be administered as i.v. infusion by the Investigator or his designee. Details and procedures of administration of study drug are described in [Section 4.1.4](#) and in the ISF.

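### As the visible text reads, the structured local tolerability check falls before each infusion, and the Day 85 infusion has no later structured check

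*Protocol*

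**What the plan says.** Section 5.3.5.2 defines the assessment: "Local tolerability will be assessed by the investigator according to" swelling, induration, heat, redness, pain or other findings. It sets no clock time and defers to the chart, "at the times indicated in the Flow Chart".

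In the Flow Chart, the row "Local Tolerability" is marked at Visits 2, 6, 8 and 10 only (Days 1, 29, 57 and 85). Table 4.1.4:1 confirms that these are the four dosing visits. The row shows no footnote marker and no pre-dose or post-dose label.

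Three further passages fix the order within a dosing visit:

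- Section 6.1, general rule for everything measured at a dosing visit: "scheduled to occur 'before' trial medication administration at dosing visits and are to be performed and completed prior to the trial drug administration".
- Section 6.2, recommended sequence: step 2 is "AE/local tolerability and concomitant therapy collection". Physical examination, the efficacy scores, ECG and blood sampling (step 7) follow.
- Section 6.2.2: blood draws "should be the last procedures performed prior to study drug administration".

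The protocol does name post-infusion measurements elsewhere. Section 5.3.2 states that "vital signs will be assessed pre-dose, at 5 minutes and approximately 120 minutes after study drug administration", and asks for about two hours of observation for hypersensitivity. Local tolerability is not mentioned there.

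**The concern.** The listed signs are reactions at the infusion site. To show what an infusion did, they have to be looked for after it. A check completed before the infusion can at best show what is left of a reaction to the previous one, about four weeks earlier, and on Day 1 there is no previous one.

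Tolerability is in the trial title and among the synopsis safety criteria, and Section 3.2 gives the main aim as to "investigate proof of concept (safety and efficacy) and tolerability of BI 655130 in patients with PPP". Section 2.3 itself lists bruising, inflammation of the vein wall and local infection as risks of the infusion catheter. If the structured check is made at a time when it cannot see these reactions, its summary by arm says little about local tolerability, and no later analysis can recover observations that were not made. If some sites check before the infusion and others after, the pooled data mix two different measurements.

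**Working it through.** The protocol gives no figure to reproduce. The check is a cross-reading followed by simple day counts.

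**Order within a dosing visit**

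1. Section 6.2: local tolerability (step 2) comes before blood sampling (step 7).
2. Section 6.2.2: blood sampling is the last procedure before the infusion.
3. Hence local tolerability comes before the infusion. Section 6.1 gives the same result as a general rule.
4. The only assessments with stated post-dose times are vital signs (5 and about 120 minutes) and hypersensitivity observation (about 2 hours). No visible text exempts local tolerability.

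**Time from each infusion to the next structured check**

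Inputs from the Flow Chart: Day 1 (no window), Day 29±3 (26 to 32), Day 57±3 (54 to 60), Day 85±3 (82 to 88). Nominal gap = next marked day − infusion day. Shortest gap = earliest next day − latest infusion day. Longest gap = latest next day − earliest infusion day.

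| Infusion | Next structured check | Nominal gap (days) | Shortest (days) | Longest (days) |
|---|---|---|---|---|
| Day 1 | Day 29, pre-dose | 29 − 1 = 28 | 26 − 1 = 25 | 32 − 1 = 31 |
| Day 29 | Day 57, pre-dose | 57 − 29 = 28 | 54 − 32 = 22 | 60 − 26 = 34 |
| Day 57 | Day 85, pre-dose | 85 − 57 = 28 | 82 − 60 = 22 | 88 − 54 = 34 |
| Day 85 | none (Visits 11 to 13 unmarked) | – | – | – |

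**Per patient, read literally**

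- 4 structured checks: 1 before any exposure and 3 about 28 days after an infusion.
- 0 of 4 infusions have a same-day structured check after the infusion.
- 1 of 4 infusions has no later structured check at all. With 60 patients, that is the 60 planned Day 85 infusions.

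**The case against.** The strongest reply is that this is unstated timing rather than a chosen design. A check for infusion-site signs on Day 1 before any drug has little purpose, so marking the row only on infusion days suggests that a check after each infusion was meant. The rule in Section 6.1 is general and not absolute, since Section 5.3.2 already departs from it for vital signs. The sequence in Section 6.2 is only recommended, applies to all visits, and pairs local tolerability with adverse event collection, which is not confined to the pre-dose period. All of this stands as an argument about intent. It does not supply a post-infusion time, and it leaves the visible text pointing the other way.

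Parts of the relevant text are also not visible. The list in Section 6.2 lacks steps 1 and 5 and breaks off within step 7, several Flow Chart footnotes are not shown, and infusion handling instructions sit in the investigator site file. A timing note could exist there. This limits confidence, although Section 5.3.5.2 points to the Flow Chart and not to the site file.

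A reader might go further and infer that the last infusion is never assessed by any means. The protocol does not support that. Adverse events are collected from consent to the end of the trial and are marked at every visit, patients are observed for about two hours after dosing, and infusion reactions have their own procedures. After the first infusion, Visits 3 and 4 (Days 4 and 8) also include a targeted physical examination. The gap concerns the structured items only.

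A reader might also infer that the structured data are bound to show almost nothing in every arm. That is a prediction about site practice and reaction rates, and the protocol gives no basis for it.

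Finally, local tolerability is neither a primary nor a secondary endpoint and is absent from the list in Section 5.3. The primary safety endpoint is drug-related adverse events. That bounds the importance of the point.

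**Conclusion.** The point holds for the structured local tolerability assessment. On the visible wording it precedes every infusion, so none of a patient's four infusions is followed by a timely structured check and the Day 85 infusion is followed by none. Adverse event reporting remains as the route by which local reactions are captured, and no primary or secondary efficacy conclusion depends on this row.

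The conclusion rests on two assumptions. First, the Flow Chart marks belong to Days 1, 29, 57 and 85. The column layout of the available copy is imperfect, but the marks line up with the Day row and their spacing fits the dosing visits. Second, no text outside the visible protocol sets a post-infusion time. If a post-infusion check was always intended, the defect is a contradiction in the text and not a design choice. The correction is the same either way, because sites working from the present wording could time the check differently.

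**What to change.** Reconcile the four places so that they say one thing:

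- Flow Chart and Section 5.3.5.2: state that local tolerability is assessed after the end of each infusion, including Day 85, within the existing post-dose observation period. The vital-signs check at about 120 minutes is one convenient anchor.
- Section 6.1: except local tolerability from the pre-dose rule, as post-dose vital signs already are in practice through Section 5.3.2.
- Section 6.2: take local tolerability out of step 2, or note that at dosing visits it follows the infusion.

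The cost is a wording change and a brief added inspection of the infusion site. No visit is added, since Section 5.3.2 already has the patient under observation for about two hours after dosing.

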6.2 DETAILS OF TRIAL PROCEDURES AT SELECTED VISITS

Study procedures to be performed at each visit are listed in the Flow Chart and respective protocol sections. Additional details on procedures at selected visits are provided below.

Measurement of vital signs should precede blood sampling and be assessed pre-dose at all dosing visits.

The following sequence of procedures at each visit (where applicable) is recommended:

2. AE/local tolerability and concomitant therapy collection
3. Physical examinations
4. pppPGA, ppPASI

6. ECG
7. Blood sampling,

6.2.1 Screening and run-in period(s)

Screening Period

Study requirements, including the procedure for the follow-up of prematurely withdrawn patients must be fully explained to the patient and written informed consent obtained prior to initiating any study-related evaluation. The importance of staying in the trial until completion of all study requirements will be emphasized. No trial procedures should be done unless the patient has consented to taking part in the trial.

Once consented, the patient is considered to be enrolled in the trial and has started screening. The patient should be recorded on the enrolment log and be registered in IRT as a screened patient. Patients will be assigned a study patient number by the RDC system once the consent is signed.

Baseline conditions and medical history will be assessed during screening.

Screening (Visit 1) should normally take place no more than 28 days before Visit 2 and be completed no less than 7 days prior to Visit 2. Visit 1 procedures may be completed over multiple physical visits, if needed.

The time window for Visit 1 may be extended at the discretion of the CML in conjunction with the TCM on a case by case basis.

Patients who have a laboratory test value that makes their participation uncertain may have the test repeated to determine eligibility; however, the result must be available prior to Visit 2 (Day 1).

Patients who fail screening following Visit 1 assessments should be registered as a screen failure in IRT. Re-screening is allowed in this trial.

For the comprehensive list of the trial procedures required at the Screening Visit (Visit 1) please refer to [Flow Chart](#).

6.2.2 Treatment period(s)

When eligibility of the patient to participate in the trial is confirmed, randomisation via IRT will be performed at Visit 2. The treatment period is from Visit 2 to Visit 10, followed by the primary endpoint visit at week 16 (Visit 11). Procedures described in the Flow Chart for each visit should be performed.

At visits during the treatment period, venepuncture (i.e. safety laboratories, should be the last procedures performed prior to study drug administration. Only after all blood specimens are collected, will each eligible patient receive a dose of the assigned trial medication. Trial medication will be administered as i.v. infusion by the Investigator or his designee. Details and procedures of administration of study drug are described in [Section 4.1.4](#) and in the ISF.

6.2.3 Follow Up Period and Trial Completion

For all randomised patients termination of trial medication and trial completion must be recorded on the corresponding CRFs.

For patients completing the randomized trial treatment regularly at week 16, safety follow-up visits will be performed at week 24 (FU1 visit) and at week 32 (End of Trial, EOT visit).

Early treatment discontinuation

Patients who discontinue treatment prematurely prior to the week 12 (last planned treatment visit), should follow the scheduled visits as defined in the [Flow Chart](#) until the End of Trial Visit at week 32.

Trial completion:

Trial completion is defined as a patient having reached the EOT visit (Week 32).

7.0 STATISTICAL METHODS AND DETERMINATION OF SAMPLE SIZE

7.1 STATISTICAL DESIGN – MODEL

This trial is a study of proof of concept in patients with palmoplantar pustulosis. It is designed as a randomised, double-blind, and placebo-controlled trial with 3 parallel groups (2 doses of BI 655130 and placebo).

The primary objective of this trial is to assess the safety and efficacy of BI 655130 in comparison to placebo in patients with palmoplantar pustulosis.

Baseline refers to the measurement recorded at randomisation (Visit 2); if data at Visit 2 is missing, then data from Visit 1 will be considered baseline. The percent reduction from baseline of the primary endpoint, at all follow-up visits, is calculated as:

$\% \text{ ppPASI reduction from baseline} = ((\text{ppPASI at baseline} - \text{ppPASI at Visit X}) / \text{ppPASI at baseline}) * 100.$

Achieving a response of X% or larger decrease from baseline in ppPASI score is denoted as ppPASIX (where X = 50). This trial is designed to demonstrate an increase in the proportion of patients who achieve a ppPASI50, the primary endpoint, for BI 655130 relative to Placebo via the unadjusted risk difference estimate at week 16.

Randomisation will be stratified by the presence or absence of plaque psoriasis. However, due to the low number of patients to be recruited into this trial, the effects of the stratification variable on the primary endpoint will be assessed only in exploratory analyses.

7.2 NULL AND ALTERNATIVE HYPOTHESES

There will be no formal hypothesis testing performed in this trial. As an exploratory Phase II trial in patients with palmoplantar pustulosis, inferences concerning the efficacy of BI 655130 will be based on the magnitude of the observed difference(s) versus Placebo on the proportion of patients who achieve a 50% reduction from baseline in the ppPASI score (ppPASI50) at Week 16, as well as on other efficacy endpoints, such as the % change in ppPASI from baseline, ppPASI75, etc.

The study has 3 treatment arms (BI 655130 900 mg, BI 655130 300 mg and placebo), and there are 2 scenarios of interest, as described below:

- (1) Scenario 1: Examines the maximum effect of (BI 655130 900 mg or 300 mg) versus Placebo
- (2) Scenario 2: Examines the effect of BI 655130 300 mg versus Placebo

A sample size justification regarding the scenarios of interest and potential decision boundaries for comparison can be found in [Section 7.7](#).

7.3 PLANNED ANALYSES

The efficacy analyses will be performed for the FAS which is based on the intent-to-treat principle, and comprises all participants who were randomised, received at least one dose during the trial, and had a baseline measurement for the primary endpoint. Efficacy analyses will be based on the planned treatment (i.e., the treatment assigned at randomisation). Safety analyses on patients who were randomised and received at least one dose during the trial will be based on the actual treatment received at the randomisation visit; this set of patients is called the Safety Analysis Set (SAF). All efficacy analyses will be conducted on the FAS. All safety analyses will be conducted on the SAF.

Important violations of the protocol will include key inclusion and exclusion violations, incorrect medications taken, compliance with study medication, concomitant use of restricted medications, and any other violations of the protocol deemed important by the study team. All decisions concerning important protocol violations will be made prior to un-blinding of the database for the final week 16 analysis. A per-protocol set (PPS) will be defined as a subset of the FAS which excludes all patients with a violation that potentially affects the Week 16 efficacy assessment.

Standard statistical parameters (number of non-missing values, mean, standard deviation (SD), median, quartiles, minimum and maximum) or frequency tables (including patient frequencies and percentages) will be calculated where appropriate.

For continuous secondary endpoints, mean changes from baseline will be analysed using a restricted maximum likelihood (REML)-based repeated measures approach. Analyses will include the fixed, categorical effects of treatment and visit, presence or absence of plaque psoriasis (yes/no), as well as the treatment-by-visit interaction, and continuous, fixed covariates of baseline “endpoint” and baseline-by-visit interaction. An unstructured covariance structure will be used to model the within-patient measurements. Exploratory confidence intervals will be based on least-squares mean differences to Placebo using a two-sided $\alpha = 0.05$.

This is an exploratory trial and formal confirmatory statistical testing will not be performed.

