4.1.5 Blinding and procedures for un-blinding

4.1.5.1 Blinding

Patients and investigators involved in trial conduct will remain blinded with regard to the randomised treatment assignments until after the final trial database lock. The randomisation code will be kept secret by Clinical Trial Support up to the final database lock. For the primary analysis which is to be performed at week 16 once all randomized patients have completed the 16-week visit, the blind status of study personnel through the remainder of the trial will be clarified in a logistics plan which is to be finalized prior to the unblind for the week 16 analysis. Please refer to [Section 7.4](#) for further details.

A partially external DMC will perform an un-blinded safety and efficacy assessment at specified intervals in order to ensure that patients are protected from potential harm, please refer to [Section 3.1.1](#). An optional interim analysis, to be performed on the primary efficacy endpoint once 50% of the total required number of patients has completed 16 weeks of study, will also be performed by the DMC. Furthermore, an interim analysis on primary, secondary and selected further efficacy endpoints, to be performed by an external vendor once 75% of the total required number of patients has completed 16 weeks of study, will additionally be done. Please refer to Section 7.4 for further details.

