An additional interim analysis will be performed once the first 75% of patients have completed 16 weeks of the study for the purpose of planning the subsequent trial(s) in PPP. This analysis will include primary, secondary, and selected further efficacy endpoints and biomarkers as well as the PK concentration data, and details of the statistical analysis will be specified in the trial statistical analysis plan. In order to protect the integrity of the continuing trial, this 75% interim analysis will be performed by a team who are external and fully independent from the trial team. The information resulting from this analysis will not be shared with patients, investigators, or with sponsor-involved trial team members. An interim analysis logistics and access plan will be prepared which will outline the team who will perform the analysis, the procedures to protect the blind, the unblinding process, and the individuals who will have access to the results and to any individual unblinded data. There are no changes to the design of the trial planned as a result of the performance of this additional interim analysis.

Once all randomised patients have completed the first 16 weeks of study, a partial database lock may be performed in order that a fast track analysis of primary and selected secondary and safety endpoints be done; a second data lock would then be done for the remaining efficacy and safety data collected up to week 16. If fast-track analysis is not performed, a single database lock will be done for safety and efficacy data collected up to week 16. At this time, the final analysis of these data through week 16 will be performed. Since the study is planned to continue through an additional 16 weeks of further follow-up, and will remain blinded, a week 16 logistics plan will be developed in order to protect the integrity of the ongoing trial data and reporting subsequent to treatment un-blind for both the fast track and the complete week 16 primary analysis. Details of the analysis to be performed for the week 16 data will be described in the TSAP which is planned to be finalized prior to achieving database lock for the optional week 16 interim analysis.

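### Section 7.3 ties the violation deadline to the final Week 16 analysis, so an optional fast-track un-blinding under Section 7.4 can come before violation and per-protocol decisions

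*Protocol*

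**What the plan says.** Protocol Section 7.3 lists what counts as an important violation and ends the list with an open category: "any other violations of the protocol deemed important by the study team". The PPS is the subset of the FAS that "excludes all patients with a violation that potentially affects the Week 16 efficacy assessment". The deadline is: "All decisions concerning important protocol violations will be made prior to un-blinding of the database for the final week 16 analysis". The same section states: "All efficacy analyses will be conducted on the FAS".

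Section 7.4 describes what may happen once all randomised patients have completed 16 weeks: "a partial database lock may be performed in order that a fast track analysis of primary and selected secondary and safety endpoints be done". It continues: "a second data lock would then be done for the remaining efficacy and safety data collected up to week 16". Without a fast track there is one lock. In either case the final analysis of the data to Week 16 is placed after this description of the locks. Section 7.4 also calls for a logistics plan to protect the ongoing trial's data and reporting "subsequent to treatment un-blind for both the fast track and the complete week 16 primary analysis".

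Section 4.1.5.1 does not fix who stays blinded after Week 16, apart from patients and investigators. It says that "the blind status of study personnel through the remainder of the trial will be clarified in a logistics plan", to be finalised before the Week 16 un-blinding.

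**The concern.** Section 7.3 clearly intends violations to be judged blind. That intention is met only if the event to which the deadline is tied is the first one that reveals treatment. With the fast track in use, it may not be. Treatment is un-blinded at the partial lock, but the deadline as worded is met by any decision taken before the later un-blinding for the final analysis.

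What is at stake is who enters the PPS, how violations are reported, and the cleaning of Week 16 endpoints not yet locked. Some of these are patient-level judgements, and the open category in Section 7.3 leaves room for discretion. If the people making them know the treatment and the primary result, a reader cannot rule out influence, even where none occurred.

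**Working it through.** The protocol gives no figure on this point, so the check is one of sequence. The sections are set side by side.

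1. **Does the fast track un-blind treatment?** Yes. Section 7.4 refers to un-blinding "subsequent to treatment un-blind for both the fast track and the complete week 16 primary analysis", which names two events.
2. **Are Week 16 data still open at the first of them?** Yes. The lock at that stage is partial, and "a second data lock would then be done for the remaining efficacy and safety data collected up to week 16".
3. **Which analysis is the final one?** Section 7.4 places the final Week 16 analysis after the second lock, or after the single lock if there is no fast track.
4. **To which event is the violation deadline tied?** Section 7.3 ties it to un-blinding for the final Week 16 analysis and does not mention the fast track.

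The order that these sections allow is: partial lock; fast-track un-blinding and analysis; violation and PPS decisions and cleaning of the remaining Week 16 data; second lock; final Week 16 analysis. Nothing in Section 7.3 forbids the third step at that place.

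**Does another section close the gap?**
- Section 4.1.5.2 lists the un-blinding events but has no separate fast-track entry.
- Section 3.1 describes a single lock for the Week 16 analysis and does not deal with the two-lock option.
- Section 3.1.1 gives data management and statistics to the sponsor. For the 75% interim, Section 7.4 requires an external team independent of the trial team. It states no equivalent for the fast track.
- Section 6.1 refers to a blinded report planning meeting. Its stated task is measurements outside the visit windows, and it is not dated against the fast track.
- Under Section 7.4 the statistical analysis plan is to be finalised before the lock for the optional 50% interim. That fixes rules early, but it does not date the decisions on individual patients.

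**What do the decisions affect?** FAS membership needs randomisation, at least one dose and a baseline value for the primary endpoint. No violation judgement enters that definition. Sections 7.3.1 and 7.3.2 use the FAS for the primary and the binary secondary endpoints. The protocol defines the PPS but specifies no analysis on it. The primary endpoint is among the fast-track analyses, so its data should already be in the partial lock, although the protocol does not list that lock's contents.

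**The case against.** The strongest reply is that the final Week 16 analysis in Section 7.3 means the analysis of all patients, as opposed to the 50% and 75% interims. Section 3.1 uses the term that way, and Section 4.1.5.2 lists only one un-blinding for the Week 16 primary analysis. Because the fast track covers the primary endpoint, its un-blinding could be taken as that event, which would put the deadline before it. This is a fair reading, but Section 7.4 names two un-blindings and places the final analysis after the later lock. The text is ambiguous at best.

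A second reply is that the logistics plan covers data and reporting after the fast-track un-blinding and may keep the relevant people blinded. It may, and its contents are not at hand. But the protocol does not commit the plan to that, and the plan does not move the deadline in Section 7.3.

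A third reply is that little depends on these decisions: the fast track is optional, the trial is exploratory without confirmatory testing, and efficacy is analysed on the FAS. This stands, and it limits the point to a minor one. It is also true that restricted medications are listed in Table 4.2.2.1:1 and that the definition of relevant rescue use is assigned to the statistical analysis plan. The remaining discretion is therefore mainly about which violations lead to PPS exclusion.

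**Conclusion.** The point holds as a gap in timing. If the fast track is used, and unless the logistics plan prevents it, violation and PPS decisions and the cleaning of the remaining Week 16 data may be done with treatment known without breaching the protocol. The wording permits this; it does not require it. The primary efficacy result on the FAS is largely unaffected, provided that the records it needs are in the partial lock. The exposure is PPS membership, violation reporting and the endpoints still open.

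Three stronger readings are tempting, and the documents do not support them.
- **That late exclusions could carry the trial across its decision thresholds of 0.15 and 0.20.** Those thresholds in Section 7.7 concern the primary-endpoint differences, which Section 7.3.1 analyses on the FAS. Nor does each PPS exclusion shift an arm by a full 5 points. With r responders of 20, dropping a non-responder raises the rate by r/19 − r/20 = r/380, and dropping a responder lowers it by (20 − r)/380. Either is at most 19/380 = 5.0 points. With an assumed 9 of 20, dropping a non-responder gives 9/19 − 9/20 = 0.474 − 0.450, or 2.4 points. The number of debatable patients is not given, so no total effect can be stated.
- **That the primary safety endpoint is exposed through judgements of drug-relatedness.** Section 5.3.6.2 gives causality to the investigator, and Section 4.1.5.1 keeps investigators blinded until the final lock.
- **That the trial is no longer double-blind.** Patients and investigators remain blinded; the gap concerns only those at the sponsor who handle the Week 16 data.

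**What to change.** In Protocol Section 7.3, state that all important-violation and PPS decisions are documented before the first Week 16 treatment un-blinding, including any fast-track un-blinding.

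In Section 7.4, state that anyone able to query or change unlocked Week 16 data stays blinded until the second lock. The logistics plan can then set out how.

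The cost is a wording change. The fast-track lock may come slightly later, because violation decisions for up to 60 patients must be complete first. If the fast track is not used, the change makes no difference to timing.
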